4.1.7. Analysis Timepoint Window and Out-of-Window Measurements

Analysis timepoint is a timing variable to be used for analyses involving timepoints. The IOP will be measured two or three times for each timepoint, and the last recorded time will be used for determining its timepoint. For each analysis timepoint, an *analysis timepoint window* is set up to determine the allowance range (Table 3).

Table 3. Analysis Timepoint and Analysis Timepoint Window

Analysis Timepoint	Timepoint Window	Analysis Timepoint Window
8:00	[7:00, 9:00]	[- 8:59]
10:00	[9:00, 11:00]	[9:00, 12:59]
16:00	[15:00, 17:00]	[13:00 -]

If there are two or more measurements that fall into the same analysis timepoint window, the measurement closest to the target assessment time will be selected for that timepoint. In the case that two measurements are closest and equidistant to the target assessment time, i.e., one is before and one is after the target assessment time, the later one will be selected for that timepoint.

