7.1. Subject Early Discontinuation/Withdrawal from the Study

An early termination occurs when a subject who provides written informed consent ceases participation in the study, regardless of circumstances, before the completion of the study. Subjects may be voluntarily discontinued from study medication or withdrawn from the study at any time for any reason. In addition, the Principal Investigator or Medical Monitor or designee may discontinue the study drug administration or terminate a subject's study participation due to any of the following reasons:

- AE (e.g., not compatible with study continuation)
- Non-compliance with study drug
- Lack of efficacy (e.g., IOP exceeds 34 mmHg in either eye after randomization)
- Progressive disease
- Protocol deviation (e.g., not fulfilling eligibility criteria)
- Pregnancy
- Voluntary withdrawal by subject at any time for any reason
- Lost to follow-up (e.g., no contact is possible)
- Death
- Other

If the study drug administration is discontinued prior to Visit 5, they should be encouraged to still participate in all follow-up study visits until Visit 5 on an observational basis.

If the study drug administration is discontinued prior to Visit 5, then to the extent possible, all procedures for Early Termination will be performed on the day of early drug discontinuation as per [Table 3](#). Subjects who are discontinued from the study early will not be replaced.

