8.1.4. Visit 3 (Week 2, Day 14 ± 3)

- Update concomitant medications and procedures/therapies.
- An authorized unmasked study staff member, other than the Investigator or Examiner should query the subject regarding dosing compliance, check the subject paper diary

of daily medication recording, and ensure subject has sufficient study medication to complete dosing through Visit 4 (Week 6).

- Query the subject regarding AEs.
- As per Schedule of Events and Procedures ([Table 3](#)), perform the following procedures or assessments immediately before the 08:00 (± 60 min) IOP measurement (all ophthalmic procedures to be performed in both eyes):
 - BCVA (before the 08:00 (± 60 min) IOP measurement)
 - If more than 10 letters in BCVA were lost compared to the screening visit, then refraction should be performed again.
 - Slit-lamp biomicroscopy (before the 08:00 (± 60 min) IOP measurement)
- Perform IOP measurement at 08:00 (± 60 min).
- Instill study medication/eye drop after the 08:00 IOP measurement in both eyes. Authorized unmasked study staff should make sure the instillation is performed. Record the morning medication in the subject diary.
- Perform IOP measurement at 10:00 (± 60 min), and 16:00 (± 60 min).
- If the subject provided written consent to provide a blood sample for a future PGx laboratory research study, collect the sample at this visit or subsequent visit prior to exit from the study.
 - Note: If a blood sample cannot be collected at this visit, it may be collected at any one of the following visits, for example, Visit 4, 5, or unscheduled or early termination visit, provided the subject has written consent prior to collection of the sample.
- Schedule the subject to return on Day 42 \pm 3 for Visit 4 (Week 6).
- Remind the subject to continue dosing according to the written instructions.
- Inform the subjects they will be reminded of the evening instillation of the study medication by a phone call a few days before Visit 4 (Week 6).
- Remind the subjects that the morning dose of Visit 4 (Week 6) will be done at the site.
- Remind the subject to bring all used and unused study medication and subject diary at Visit 4 (Week 6).

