9.7. Efficacy Analyses

Unless specified otherwise, for subjects who discontinue from the study medication per protocol before the Study Exit, the IOP data collected after the study medication discontinuation with any use of non-study IOP lowering medication or surgery will be censored from all efficacy analyses.

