12.3.7. Intraocular Pressure

IOP will be performed at each visit. At visit 1 (Screening)/1a (Optional visit), IOP can be measured at any time. For Visit 2 (Baseline, Day 1) to Visit 5 (Month 3) Exit/Early Termination, IOP measurements will be scheduled for 08:00 (± 60 min), 10:00 (± 60 min), and 16:00 (± 60 min).

IOP will be measured using calibrated manual Goldmann applanation contact tonometer with the subject in a sitting position. The same Goldmann contact tonometer employing the investigator's standard technique will be used throughout the study. Measurement will be performed preferably by the same authorized study staff throughout the study. Study staff who performs the IOP measurement must have at least 2 years of experience in IOP measurement.

The right eye is always tested first. At least two, and sometimes three, consecutive measurements are made to obtain a determination of IOP. Each IOP measurement and the clock time of IOP measurement will be recorded in the subject's source document.

A single measurement is made as follows:

- The study staff adjusts the force on the tonometer dial to an initial setting corresponding to 10 mmHg. The slit-lamp magnification is set at 10X. The light source is positioned at an angle of approximately 45°, and the aperture is maximally opened. A cobalt blue filter is employed.
- After instillation of a topical anesthetic, a fluorescein paper strip is placed near the lateral canthus in the lower conjunctival sac. Once the lacrimal fluid is sufficiently colored, the paper strip is removed. Alternatively, one drop of premixed fluorescein and anesthetic (Fluress, Barnes Hind) may be instilled. The study staff should use the same technique each time, be it a paper strip or a pre-mixed eye drop.
- The subject and slit-lamp are adjusted so that the subject's head is firmly positioned on the chin rest and against the forehead rest without leaning forward or straining. Tight-fitting neckwear is loosened. The subject is asked to look straight ahead at a distant object or fixation target. If it is necessary to hold the eyelids open, the study staff holds the eyelids against the orbit rim, taking care not to apply any pressure to the globe. The subject is cautioned not to hold his breath.

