4.2.2. Efficacy Measure

IOP (in mmHg) is the efficacy measure for this study. For the IOP at each timepoint of measurement, a mean of two consecutive measurements using the Goldmann applanation tonometer will be used. If the two measurements differ by 3 mmHg or more, then a third measurement will be made, and the median of the three consecutive measurements will be used.

The mean diurnal IOP at each visit is defined as the mean of the three scheduled timepoints 8:00, 10:00, and 16:00 at the visit. If there are one or more missing IOP measurement at timepoints, the mean diurnal IOP will not be calculated.

To assess the efficacy of DE-126, the mean/median IOP at each scheduled timepoint (8:00, 10:00, 16:00) and the mean diurnal IOP in the study eye will be analyzed. In addition, changes and percent changes from baseline in IOP at each timepoint and the mean diurnal IOP in the study eye will also be analyzed.

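### SAP 4.1.7 places each IOP set by the clock time of its last reading, so an 08:00 set ending at 09:00 or later loses its slot and can, in some cases, be analysed as the 10:00 value

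*SAP*

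**What the plan says.** SAP 4.1.7 explains how each set of two or three IOP readings is given its analysis timepoint: "the last recorded time will be used for determining its timepoint". The table in that section lists two windows for each timepoint:

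- 08:00: scheduled 7:00 to 9:00; analysis, anything up to 8:59.
- 10:00: scheduled 9:00 to 11:00; analysis 9:00 to 12:59.
- 16:00: scheduled 15:00 to 17:00; analysis from 13:00 on.

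If two sets fall in one analysis window, "the measurement closest to the target assessment time will be selected for that timepoint"; on a tie, "the later one will be selected for that timepoint". Nothing in the section keeps a set at the timepoint for which it was collected, or takes account of whether it was taken before or after the dose. The section is not limited to post-baseline visits.

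Three other provisions bear on the result. SAP 4.2.2 says: "If there are one or more missing IOP measurement at timepoints, the mean diurnal IOP will not be calculated". SAP 8.1.1.1 fits a separate MMRM for each clock timepoint, with baseline IOP as covariate, so the 08:00 slot supplies three of the nine co-required comparisons. Protocol 8.1.4 orders the visit as follows: "Instill study medication/eye drop after the 08:00 IOP measurement in both eyes". Sections 8.1.5 and 8.1.6 say the same for Visits 4 and 5.

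**The concern.** A set collected as the 08:00 measurement but ending at 09:00 or later is filed under 10:00. There it competes with the true 10:00 set, and one of the two is discarded. Unless another set fills the 08:00 window, the 08:00 value is missing although it was measured, and the mean diurnal IOP for that visit goes with it. At Month 3 that is the key secondary endpoint. A set begun before 09:00 can end after it, because a third reading is required when the first two differ by 3 mmHg or more.

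The second consequence is a wrong value, not a missing one. At Visits 3 to 5 the 08:00 set is taken before the morning drop given on site. If it wins the 10:00 slot, a pre-dose pressure is analysed as post-dose. That drop is vehicle in one arm and timolol in the other, so the misfiling bears on what the 10:00 comparison measures.

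**Working it through.** **Windows.** Inputs are the ±60 minute tolerance (Protocol 12.3.7) and the SAP 4.1.7 table. Nominal time ±60 minutes gives 07:00–09:00, 09:00–11:00 and 15:00–17:00, which reproduces the table's scheduled windows. Set against the analysis windows, only one permitted minute falls outside its own slot: 09:00 for the 08:00 timepoint.

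**Both sets inside their scheduled windows.** Minute by minute, with the 10:00 set ending later, there are 121 × 121 − 1 = 14,640 pairs. The 08:00 value is kept in 14,520 and lost in 120, all with the 08:00 set ending at exactly 09:00. Substitution occurs in none: a set at 09:00 is 60 minutes from 10:00, the true set is at most 60 minutes away, and the tie at 11:00 goes to the later set.

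**08:00 set ending after 09:00.** Let it end x minutes after 09:00 (x < 60), and let the true 10:00 set end s minutes later, after 10:00 and before 13:00.

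- Distance of the 08:00 set from 10:00: 60 − x.
- Distance of the true set from 10:00: x + s − 60.
- The 08:00 set is chosen when 60 − x < x + s − 60, that is, s > 120 − 2x.

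For 09:10, x = 10 and s must exceed 100. A true set ending at 10:50 ties and is kept. One ending at 10:51 (51 minutes away against 50) is replaced, although 10:51 is inside its own scheduled window. The 08:00 set is also used when the true 10:00 set is missing or ends at 13:00 or later. In every case the 08:00 slot is left empty unless another set falls in it.

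**Size of the loss.** Inputs from the sample-size section: 140 per arm, SD 4.0 mmHg, margin 1.5 mmHg, true difference 0, two-sided 5%. The loss rates are assumed, equal in both arms. Power at one 08:00 timepoint = Φ(1.5 / (4.0 × √(2/n)) − 1.96).

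- No loss, n = 140: Φ(3.137 − 1.96) = 88.1%.
- 2% lost, n = 137.2: Φ(3.106 − 1.96) = 87.4%.
- 5% lost, n = 133.0: Φ(3.058 − 1.96) = 86.4%.
- 5% lost at the visit and, independently, 5% at Visit 2, n = 140 × 0.95 × 0.95 = 126.35: Φ(2.981 − 1.96) = about 84.6%.

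The last line arises because a Visit 2 08:00 set lost by the same rule removes the covariate for the 08:00 model, and SAP 4.2.3 gives no specific rule for an empty Visit 2 slot. These are unadjusted single-timepoint figures and do not reconstruct the plan's 70%; read the change, not the level.

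For mean diurnal IOP, assuming a within-day correlation of 0.6, the SD is 4.0 × √((1 + 2 × 0.6)/3) = 3.43. The same formula gives 95.6%, 95.2% and 94.6% at 0%, 2% and 5% loss.

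**Size of a substitution effect.** With equal substitution rates p in the two arms, bias at 10:00 = p × (between-arm difference in the 08:00-minus-10:00 change). With p of 1% to 5% and a difference of 0 to 2 mmHg, all assumed, the range is 0 to 0.05 × 2 = 0.10 mmHg.

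**The case against.** The strongest reply is that filing by actual time is a convention, not a mistake. SAP 4.1.6 does the same for visits, and the endpoint is IOP at stated clock times, so declining to call a set ending at 09:40 an 08:00 value is defensible. The scheduled windows share the minute 09:00, so any clock rule must give it to one side: moving the boundary to 9:00 would clip a 10:00 set ending at exactly 09:00 and still lose 08:00 sets ending at 09:01 or later. Late sets can also be recorded as time-window deviations (SAP 7.4) and removed from the per-protocol set under masked review (SAP 5).

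Much of this stands. It supports leaving a very late set out of the 08:00 analysis. It does not support using a pre-dose set as the post-dose value, and the deviation review does not correct the primary analysis, which uses the full analysis set. A set ending at exactly 09:00 is not a deviation at all.

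A reader might infer that the rule misfiles pre-dose readings even when sites keep to the windows. It does not when both sets end in window. A reader might also infer that, because the morning drop is active only in the timolol arm, substitution favours DE-126. The documents give neither the 08:00-to-10:00 change by arm nor any reason for unequal substitution rates: both arms follow one schedule and examiners are masked.

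**Conclusion.** The point holds as a minor flaw in the assignment rule. When both sets end in window, it costs one clock minute and acts only by loss. Outside that, an 08:00 set ending after 09:00 loses its slot and can replace the true 10:00 set, putting a pre-dose reading into a post-dose analysis.

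The effect is probably small. Under the assumed 2% to 5% loss, power at one 08:00 timepoint drops by 0.7 to 1.7 percentage points. It would be tempting to call that an upper bound, since the MMRM also draws on other visits. It is not one, because loss of the Visit 2 covariate works the other way (about 84.6% with 5% lost at both). The documents contain no set timings, so neither the frequency nor the split between discard and substitution is known. No direction of bias is claimed.

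**What to change.** Amend SAP 4.1.7 and its table before unmasking:

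- Assign each set to the scheduled timepoint at which it was collected, at Visit 2 and at every post-baseline visit.
- State that a set collected as the 08:00 measurement never fills the 10:00 slot.
- Use clock time only to flag out-of-window sets for the masked deviation and per-protocol review.
- If the sponsor prefers to keep a clock-time limit in the full analysis set, treat a set beyond it as missing and do not move it to another timepoint.

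The scheduled label is a better key than time since dose. Protocol 7.1 says of subjects who stop study drug early that "they should be encouraged to still participate in all follow-up study visits until Visit 5 on an observational basis", and Protocol 9.7 censors their later IOP only where non-study pressure-lowering treatment was used. Such visits may have no morning dose to count from.

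The cost is one paragraph and its table. The downside is that some out-of-window readings stay under their scheduled timepoint in the full analysis set. One check is needed: Protocol 12.3.7 says "Each IOP measurement and the clock time of IOP measurement will be recorded" in the source document, but the documents do not show the eCRF layout, so the sponsor should confirm that the scheduled-timepoint label is captured there.

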4.2. Efficacy-Related Definitions

4.2.1. Study Eye

The *study eye* will be the eye that qualifies per eligibility criteria at Visit 2 (Baseline, Day 1). If both eyes meet the eligibility criteria, the eye with the higher mean diurnal IOP at Visit 2 (Baseline, Day 1) will be designated as the study eye. For example, IOP must be ≥ 22 mmHg at all IOP measurement time-points (08:00, 10:00 and 16:00). If both eyes meet the eligibility criteria and have the same mean diurnal IOP, the right eye will be designated as the study eye.

4.2.2. Efficacy Measure

IOP (in mmHg) is the efficacy measure for this study. For the IOP at each timepoint of measurement, a mean of two consecutive measurements using the Goldmann applanation tonometer will be used. If the two measurements differ by 3 mmHg or more, then a third measurement will be made, and the median of the three consecutive measurements will be used.

The mean diurnal IOP at each visit is defined as the mean of the three scheduled timepoints 8:00, 10:00, and 16:00 at the visit. If there are one or more missing IOP measurement at timepoints, the mean diurnal IOP will not be calculated.

To assess the efficacy of DE-126, the mean/median IOP at each scheduled timepoint (8:00, 10:00, 16:00) and the mean diurnal IOP in the study eye will be analyzed. In addition, changes and percent changes from baseline in IOP at each timepoint and the mean diurnal IOP in the study eye will also be analyzed.

4.2.3. Baseline Score

For any measure, the *baseline score* is the last observed measurement or derived score prior to the first dose of study medication.

4.2.4. IOP Response Endpoints and Response Rate

Four IOP response endpoints shown in Table 3 will be evaluated at each post-Baseline visit of Week 2 (Visit 3), Week 6 (Visit 4), or Month 3 (Visit 5).

For a response endpoint, the response rate at a post-Baseline visit is calculated as the proportion of subjects who met the response criterion at the visit.

Table 3 Response Endpoints

Response Endpoint	Response criteria in mean diurnal IOP
IOP 20% response	Percent reduction from Baseline \geq 20%
IOP 25% response	Percent reduction from Baseline \geq 25%
IOP 30% response	Percent reduction from Baseline \geq 30%
IOP \leq 18 mmHg response	Mean diurnal IOP \leq 18 mmHg

4.3. Safety-Related Definitions

4.3.1. Adverse Event

Events reported on the AE electronic Case Report Form (eCRF) will be assessed according to the recently amended Food and Drug Administration regulations 21 CFR Parts 312 and 320.

Under Protocol 012601IN, an AE is defined as any untoward medical occurrence that occurs in a study subject, regardless of the suspected cause and regardless of timing of study medication administration. An *on-study* AE can occur any time after the date of informed consent through the last study visit. An AE will be considered as *treatment-emergent* if the AE occurred on or after the treatment start date up to the 2 days (twice the scheduled dosing interval) after treatment end date. Treatment-emergent AEs are a subset of on-study AEs. Both on-study and treatment-emergent AEs will be recorded, but only treatment-emergent AEs will be tabulated.

The severity of each AE will be graded by the Clinical Investigator as Mild, Moderate, or Severe.

Each AE will be classified into a system organ class (SOC) and coded to a preferred term (PT) using Medical Dictionary for Regulatory Activities (MedDRA), version 23.1 published in 2020.

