4. STUDY DESIGN

4.1. Overall Study Design

This is a Phase IIb, randomized, double-masked, active-controlled, parallel-group, and multicenter study assessing the efficacy and safety of DE-126 ophthalmic solution 0.002% compared with Timolol maleate ophthalmic solution 0.5% in subjects with POAG or OHT.

[figure not shown]
Subjects diagnosed with POAG or OHT who meet eligibility criteria at Visit 1 (Screening) will washout of their current topical IOP-lowering medication(s) if any. After completing the required washout period, subjects will return for Visit 2 (Baseline, Day 1). Subjects who meet all eligibility criteria at baseline will be randomized to receive treatment for 3 months.

Approximately 294 adult subjects with POAG or OHT who meet all eligibility criteria will be randomized in a 1:1 ratio to receive either:

- DE-126 Ophthalmic Solution 0.002% QD (20:00) and Vehicle QD (08:00), or
- Timolol Maleate Ophthalmic Solution 0.5% BID (20:00 and 08:00)

In the Double-Masked Treatment Period, Timolol maleate ophthalmic solution 0.5% will be used as active control.

Figure 1: Study Design

See the study design diagram in [Figure 1](#). This study will consist of a Screening Period of up to 35 days including a washout period of up to 28 days (+ 7 days window) and a 3-month Double-Masked Treatment Period.

At the Screening visit (Visit 1), subjects will be screened against the inclusion and exclusion criteria. Eligible subjects will be instructed to discontinue use of all IOP-lowering medications, if any, during a washout period as follows (up to +7 days as a window is allowed):

- Miotics: 7 days
- CAIs: 7 days
- Alpha agonists: 14 days
- Alpha/beta agonists: 14 days
- Alpha antagonists (α 1 blocker): 28 days
- Beta antagonists (β blocker, including $\alpha\beta$ blockers): 28 days
- PGA: 28 days
- Rho kinase inhibitor: 28 days
- Combination drugs: The longest washout period of the individual component will be used.

Please note: Subjects are only allowed to be treated with a maximum of two active ingredients for IOP reduction prior to screening.

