^b Informed Consent Form must be signed and dated before study procedures are performed. Informed consent for the optional PGx laboratory research study may be obtained at any visit prior to the study exit.

^c Prostaglandin naïve subjects are defined as subjects who are not known to have used prostaglandin as their glaucoma treatment. The previous use of prostaglandin should be confirmed by either subject's medical records or subject history.

^d AE will be recorded starting after the signing of the informed consent form until 2 weeks post Last Study Drug Administration. Regardless of the source of the reported occurrence of an AE in a subject, the masked investigator will assess the causality of the AE.

^e A urine pregnancy test will be conducted for all female subjects of childbearing potential.

^f Vital signs (resting blood pressure and pulse rate) will be collected in sitting position anytime at Visit 1 (Screening), and approximately at 08:00 for Visit 2 (Baseline, Day 1), and Visit 5 (Month 3)/exit or early termination before the morning dose.

^g Refraction will be performed at the screening visit anytime. If more than 10 letters in BCVA are lost compared to the screening visit, then refraction should be performed again. BCVA examination will be completed before IOP measurement at 08:00.

^h Slit-lamp Biomicroscopy examination must be completed before IOP is measured at 08:00. Aqueous flare and cell evaluation will be performed before fluorescein instillation.

ⁱ IOP measurements using Goldmann applanation tonometer will be performed at 08:00 (±60 min), 10:00 (±60 min), and 16:00 (±60 min) at all visits except for Visit 1 (Screening), and Optional Visit 1a (mid-washout).

^j Pachymetry will be performed after IOP measurement at Visit 1 (Screening).

^k If gonioscopy was performed within 3 months (90 days) prior to screening and was documented in the subject's records, no additional screening gonioscopy examination is necessary. If needed, Gonioscopy will be performed after IOP measurement at Visit 1 (Screening).

^l If visual field test was performed within 3 months (90 days) prior to screening and was documented in the subject's records, no additional screening visual field test is necessary.

^m Ophthalmoscopy with pupil dilated will be performed at Visit 1 (Screening) anytime, Visit 2 (Baseline), and Visit 5 (Month 3)/exit or early termination at the 16:00 (± 60 min) after IOP measurements.

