The primary AE in this example is orthostatic hypotension. The fall, head trauma, and neck pain should be described in the narrative description of the case.

- For intermittent events (e.g., intermittent headache), the event onset date should be recorded as the date the subject first started to experience the event and resolution date should reflect when the last occurrence resolved or stopped. Separate AEs for each event should not be recorded. For example, if a subject experienced headache on 14SEP2015 lasting for three hours, then subsequently experienced intermittent episodes of headache every day for approximately 3 hours until 21SEP2015, then the AE date of onset is 14SEP2015 and the resolution date is 21SEP2015.
- For intermittent events, record the maximum severity of the individual events. For example, if a subject complains of intermittent headaches for one week and the severity of each headache ranges from mild to moderate, then the severity would be moderate.
- For intermittent hospitalizations occurring for a primary AE (e.g., in a subject with multiple sclerosis, commonly known for its relapsing and remitting course, in some cases leading to multiple hospital confinements), the subsequent hospitalizations should be described in the narrative description of the case.
- If treatment was initiated, include the treatment and duration of the medication(s) in the eCRF.

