8.6.5. Time Period and Frequency for Collecting AE and SAE Information

AEs and SAEs will be monitored for and collected at the time points specified in Schedule of Events and Procedures ([Table 3](#)), from the signing of the ICF until the subject withdrawal or the scheduled exit visit. (Note: Although AEs will be monitored for and collected prior to study medication administration, the statistical data analysis will determine and summarize treatment-emergent AEs, i.e., those AEs that began or worsened in severity after the first study medication administration.)

All SAEs will be recorded and reported to Santen or designee immediately and under no circumstance should this exceed 24 hours, as indicated in [Section 12.4](#), Appendix D. The investigator will submit any updated SAE data to Santen within 24 hours of it being available.

Investigators are not obligated to monitor for new AEs or SAEs after conclusion of the study participation. However, if the investigator learns of any SAE, including a death, at any time after a subject has been discharged from the study, and he/she considers the event to be reasonably related to the study medication or study participation, the investigator must promptly notify Santen.

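### The SAP's treatment-emergent rule omits the worsening clause in Protocol 8.6.5, so an AE that began before the first dose and worsened on study drug can be missing from the AE tables

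*SAP*

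**What the plan says.** Protocol 8.6.5 notes that AEs are collected before dosing but that the analysis will determine and summarise the treatment-emergent ones, defined as "those AEs that began or worsened in severity after the first study medication administration".

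SAP 4.3.1 calls an AE treatment-emergent "if the AE occurred on or after the treatment start date", with a cut-off 2 days past the end of treatment, and adds that "only treatment-emergent AEs will be tabulated". SAP 9.1, which sets out the AE tables, contains no rule on worsening. SAP Section 1 says that the plan applies to Protocol Amendment 1, the version containing the definition above.

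On recording, footnote d of the protocol's schedule (Section 4.4) says: "AE will be recorded starting after the signing of the informed consent form until 2 weeks post Last Study Drug Administration". Protocol 8.6.1.3 asks for the maximum severity of each AE. For intermittent events it says that "the event onset date should be recorded as the date the subject first started to experience the event" and that "Separate AEs for each event should not be recorded". Appendix E gives the AE form one onset date and one maximum severity. It sends a severity range within an intermittent event to the comment section and lists no item for the date of a worsening.

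**The concern.** The two documents define the main safety population of events differently, and the SAP's version is narrower. AE collection opens at consent, and screening with washout can last up to 35 days, so some AEs can start before any study drug is given. If one of these worsens on drug, the protocol promises to count it and the SAP rule does not.

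The safety objective is a comparison of the arms, and safety is summarised descriptively without testing, so the AE tables carry much of that comparison. An omitted on-drug worsening would be lost from the overall, SAE, suspected adverse reaction (SAR), ocular and non-ocular, relationship and maximum-severity summaries. The SAP paragraph also cites Protocol 012601IN, the earlier dose-finding study. That suggests the definition may have been carried over, although the documents do not say so.

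**Working it through.** No figure in the plan bears on this point, so there is nothing to reproduce. The check applies both definitions to one record. The days are assumed for illustration.

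**Inputs**
- Onset on Day -10, mild, after consent and during washout.
- First dose on Day 1, since dosing starts on the evening of Visit 2 (Protocol 4.1).
- Worsening to severe on Day 20.
- Last dose on Day 90, so the SAP's end limit is 90 + 2 = Day 92.

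**Case A: one record, onset date kept at Day -10**

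| Rule | Test | Result | Count in AE tables |
|---|---|---|---|
| Protocol 8.6.5 | Began after first dose? No. Worsened after first dose? Day 20 is after Day 1: yes. | Treatment-emergent | 1 |
| SAP 4.3.1 | Dated between Day 1 and Day 92? Day -10: no. No second test. | Not treatment-emergent | 0 |

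**Case B: the worsening is entered as its own AE dated Day 20**

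| Rule | Test | Result | Count in AE tables |
|---|---|---|---|
| Protocol 8.6.5 | Began after first dose: yes | Treatment-emergent | 1 |
| SAP 4.3.1 | Day 1 ≤ Day 20 ≤ Day 92: yes | Treatment-emergent | 1 |

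The rules therefore disagree only when the event stays in one record. For intermittent events Protocol 8.6.1.3 points to one record. For continuous events neither document says what to do when an AE already on file worsens after the first dose.

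**Can the protocol rule be derived from the recorded items?** The AE items named in Protocol 8.6.1.3 and Appendix E give an onset date and a maximum severity. An event that started on Day -10 and peaked before dosing, and one that started on Day -10 and peaked on Day 20, can carry the same onset date and the same maximum severity. Those two items cannot separate them. Adding the worsening words to the SAP is necessary but does not by itself make the rule programmable.

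**What else would show the Case A event?** SAP 9.1 lists AEs, so the event would appear there. If it is a slit-lamp sign, SAP 9.3 tabulates improvement, worsening or no change from baseline by visit and lists worsening of 2 units or more. Baseline is the last value before the first dose (Protocol 8.4; SAP 4.2.3). Slit-lamp grades are taken at Visits 2 to 5, before the 08:00 IOP measurement.

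**The case against.** Four arguments limit the point.

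1. **The SAP says occurred, not began.** This is true, and an exacerbation could be said to occur on its own date. But the AE form offers a single start date to test and the SAP names no other, so onset is the workable reading. If worsening was meant, the SAP should say so.

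2. **Worsening can be an AE in its own right.** Protocol Appendix D includes the exacerbation of a chronic or intermittent pre-existing condition among events that meet the AE definition. Conditions present at consent are taken as history, so their worsening on drug can be entered with an on-treatment date and would pass the SAP rule (Case B). This stands and narrows the gap. It does not close it, because Appendix D does not tell sites to open a second record for an AE already recorded during washout.

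3. **Hyperemia is covered elsewhere.** Conjunctival hyperemia was the most common adverse reaction in the earlier Phase IIb study, so a reader might infer that the SAP rule hides the drug's best-known effect. The documents do not support that. Hyperemia is graded 0 to 3 at each treatment-period visit and its change from baseline is tabulated. What those tables lack is symptoms, non-ocular events, seriousness and relationship, and anything between scheduled examinations.

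4. **The exposed set is narrow.** The AE must start after consent and before first dose, persist or recur, worsen on drug, and stay in one record. The 35 days are a maximum, and treatment-naïve subjects may combine Visits 1 and 2, which leaves almost no pre-dose window. This stands as a limit on size, not on the conflict between the definitions.

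**Conclusion.** The conflict is real. SAP 4.3.1 drops half of a definition to which the protocol commits the analysis, and an affected event is counted once under one rule and not at all under the other. The result rests on two assumptions: that occurrence in the SAP means the recorded onset date, and that the event is kept as one record.

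The consequence is bounded. It concerns the AE tables, mainly for symptoms, non-ocular events, and the seriousness and relationship summaries. It does not touch the efficacy analyses, and no planned safety test changes because there is none.

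A reader might infer three stronger things. The documents support none of them:
- That the event vanishes from the report: it remains in the AE listing, and slit-lamp worsening is tabulated.
- That a given number of subjects is missed: neither the rate of pre-dose AEs nor the share that worsen is stated, so any count would rest on assumed rates.
- That the omission favours DE-126: a differential effect is possible, but no figure in the documents shows one.

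This is worth correcting before unmasking because it is cheap and restores agreement with the protocol.

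**What to change.** 1. In SAP 4.3.1, define a treatment-emergent AE as one that began on or after the treatment start date, or began earlier and worsened in severity on or after that date. Leave the SAP's existing end limit unchanged.

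2. State in the SAP how worsening is identified: a separate AE record dated at the worsening, or a dated change in severity within the record. Maximum severity alone is not enough.

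3. If separate records are used, clarify Protocol 8.6.1.3 so that its single-record rule for intermittent events does not apply across the first dose. An instruction in the eCRF completion guidelines alone would contradict the protocol text.

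**Cost:** one sentence in the SAP for the definition and one for the identification rule. In addition, the separate-record route needs a short protocol clarification with site instruction, and the dated-change route needs a date item on the AE form if none exists. No visits or procedures change. Step 1 restores the protocol's definition without waiting for step 3, but how completely it can be applied depends on step 2.
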